9.4 Interim and Final Analyses

An unblinded interim assessment for sample size re-estimation (SSR) will be performed on the primary endpoint in each arm of the study by an independent statistician.

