Following the “promising zone” algorithm in Mehta and Pocock (2011), if the conditional power based on the planned final sample size of 110 patients is <42% or >80% at the interim stage, the study will continue as is (there will be no stoppage of the study for futility nor will there be a sample size increase). If the conditional power is between 42-80% (the promising zone), the sample size may then be re-estimated using the method described by Wang et al (2002) in order to maintain 80% conditional power without increasing the Type I error (probability of a false positive result) of the study. Specifically, the total revised sample size per group, M' required to achieve a conditional power of 80% to assess non-inferiority at the final analysis using a non-inferiority margin of 10% is found by solving the following equation for M' :

$$Z_{0.20} \sqrt{1 - \frac{r}{M'}} + Z_{\tau} \sqrt{\frac{M'}{r}} - Z_{1-\alpha} = 0$$

[figure not shown]
where $Z_{0.20}$ is the 20th percentile of the standard normal distribution (corresponding to the desired 80% conditional power) and where all other variables in this equation are defined above. M' will not exceed 166 patients for the DFU arm. This formula

assumes the interim observed effect size between treatments is the true effect size between treatments.

Results of the interim assessment will be presented by the independent statistician to a select Sponsor group. The report to the Sponsor will state if additional sample is required to achieve a conditional power of 80%, and if so, how many additional patients. If additional sample size is required, the Sponsor will make a decision to either enroll the additional patients or not enroll and accept that the primary endpoint may be under-powered. The independent statistician's report containing the results that led to the independent statistician's recommendation will be kept confidential within the select Sponsor group.

The following decision rules outline the possible outcomes of the interim analysis:

1. If the test for $CP_{ni} < 0.42$ or ≥ 0.8 , then there is no increase in the sample size and the trial will be completed on a minimum of 110 enrolled patients, as scheduled.

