2. If the test for conditional power is $0.42 \leq CP_{ni} < 0.8$, then the sample size will be increased by just the right amount such that CP_{ni} is increased to 0.8, under a cap of 166 patients. The range $0.42 \leq CP_{ni} < 0.8$ is called the promising zone for non-inferiority. Specifically, if CP_{ni} is in its promising zone, this decision rule increases the sample size by the smallest of 166 patients or the number needed to boost CP_{ni} to 0.8.

CP=Conditional Power
Probability of success (statistical significance) at the end of the trial given current data trend

[figure not shown]

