9.4.2 VLU Arm

The interim analysis for the VLU arm will be performed independently of the interim analysis for the DFU arm, but it will be very similar in nature.

In the VLU arm, the analysis will be conducted when ~50% of the mITT population (30 patients) have been enrolled and completed the primary endpoint evaluation. The methods will be the same as described above. M` will not exceed 90 patients for the VLU arm.

The following decision rules outline the possible outcomes of the interim analysis:

1. If the test for CPni < 0.43 or ≥ 0.8 , then there is no increase in the sample size and the trial will be completed on a minimum of 60 enrolled patients, as scheduled.
2. If the test for conditional power is $0.43 \leq \text{CPni} < 0.8$, then the sample size will be increased by just the right amount such that CPni is increased to 0.8, under a cap of 90 patients. The range $0.43 \leq \text{CPni} < 0.8$ is called the promising zone for non-inferiority. Specifically, if CPni is in its promising zone, this decision rule increases the sample size by the smallest of 90 patients or the number needed to boost CPni to 0.8.

CP=Conditional Power
Probability of success (statistical significance) at the end of the trial given current data trend

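### In the promising zone the plan makes the sample-size increase both optional and automatic, and it gives unblinded interim results to a Sponsor group that it neither defines nor separates from trial conduct

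*Combined protocol and SAP*

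**What the plan says.** **The rule for N.** Section 9.4.1 says that in the promising zone "the sample size may then be re-estimated", and then "If additional sample size is required, the Sponsor will make a decision to either enroll the additional patients or not enroll", accepting possible loss of power in the latter case. Sections 1 and 3 are also permissive about the increase. Decision rule 2 for DFU is not: "then the sample size will be increased by just the right amount", up to 166 patients. Section 9.4.2 carries the DFU methods over to VLU and repeats the rule: "then the sample size will be increased by just the right amount such that CPni is increased to 0.8", up to 90 patients.

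**Who sees the results.** Section 9.4: "An unblinded interim assessment for sample size re-estimation (SSR) will be performed on the primary endpoint" in each arm, by an independent statistician. Section 9.4.1: "Results of the interim assessment will be presented by the independent statistician to a select Sponsor group". It then describes a limited message: "The report to the Sponsor will state if additional sample is required to achieve a conditional power of 80" percent and, if so, how many patients. The statistician's report, with the results behind the recommendation, "will be kept confidential within the select Sponsor group". The group is mentioned only in 9.4.1.

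**The concern.** Two things are left open that a sample-size re-estimation should close before anyone sees unblinded data.

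1. With conditional power in the zone, one part of the plan allows N to stay as planned and another requires it to rise. No criteria for declining are given, so the choice would be made with the interim result in hand.

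2. The group receives the results and not only a target. Nothing says who its members are or keeps them out of running the trial. The Sponsor or its representatives monitor the sites (Section 12), the Sponsor may suspend or terminate part of the study (Section 13), and some imputation variables for the primary endpoint are still to be chosen (Section 9.6). People who know the interim effect could be those who do these things. No independent data monitoring committee is described.

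**Working it through.** **Inputs.** Sections 9.3.1 and 9.3.2: closure rates 75% vs 60% (DFU) and 75% vs 50% (VLU), margin 10 points, one-sided alpha 0.05, power 0.80, 20% loss. Section 5.7: 1:1 allocation. Sections 9.4.1 and 9.4.2: interim at 56 and 30 patients, zones from 0.42 and 0.43 up to 0.80, caps 166 and 90. I read the caps as arm totals, so interim/planned/cap per group is 28/55/83 (DFU) and 15/30/45 (VLU).

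**The plan's own figures reproduce.**
- DFU: Farrington-Manning n = 43.1, hence 44 per group; power at 44 is 0.807; 88/0.8 = 110.
- VLU: n = 23.1, hence 24 per group; power at 24 is 0.814; 48/0.8 = 60.
- Lower zone limits from the plan's formulas and caps: 0.420 (DFU, stated 0.42) and 0.4215 (VLU, stated 0.43).

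**Zone in terms of the interim statistic.** Since B_τ = Z_τ√τ, conditional power is CP = 1 − Φ[(1.645 − Z_τ/√τ)/√(1 − τ)]. Solving for Z_τ gives Z_τ = √τ × [1.645 + Φ⁻¹(CP)√(1 − τ)].
- DFU, τ = 28/55 = 0.509: the zone is Z_τ from 1.073 to 1.594.
- VLU, τ = 15/30 = 0.5: the zone is Z_τ from 1.075 to 1.584.

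**Taking versus declining the increase.** I enumerated all binomial outcomes exactly, with the Farrington-Manning statistic at interim and final. M' came from the plan's equation, rounded up and capped. Interim groups were equal and every enrolled patient was counted.

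| Design rates | DFU | VLU |
|---|---|---|
| Probability of the zone | 0.159 | 0.122 |
| Success in zone, taken / declined | 0.947 / 0.833 | 0.956 / 0.838 |
| Overall power, taken / declined | 0.902 / 0.884 | 0.895 / 0.880 |
| Mean increase in zone (total patients) | 45.6 | 26.6 |

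Check: 0.159 × (0.947 − 0.833) = 0.018 for DFU and 0.122 × (0.956 − 0.838) = 0.014 for VLU. These match the differences in overall power up to rounding.

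**With 20% loss, counting evaluable patients only** (interim/final/cap per group), overall power taken / declined:
- DFU: 22/44/66 gives 0.834 / 0.817; 28/44/66 gives 0.837 / 0.817.
- VLU: 12/24/36 gives 0.829 / 0.807; 15/24/36 gives 0.833 / 0.807.

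**Type I error.** At a true difference of −10 points and a control rate of 0.50 (DFU), always declining gives 0.0499 and always taking gives 0.0494. Picking whichever option is more likely to reject at every interim outcome gives 0.0506. For null control rates from 0.40 to 0.80 in both arms, that adverse choice adds at most 0.0007 over always declining. At some rates the error exceeds 0.05 even when the increase is always declined (for example 0.0550, DFU, control rate 0.65). That comes from the asymptotic test, not from the option.

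**What the target alone reveals.** Under design-rate variances, a revised DFU total of 162, 142 or 126 corresponds to Z_τ of about 1.37, 1.45 or 1.52, and to an observed difference of about +7, +8 or +9 points. A total at the cap of 166 shows only that conditional power lies between 0.42 and about 0.64.

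**Access.** No calculation applies. Section 9.4.1 describes both a report limited to need and number, and a presentation of results with a results report held by the group. The second makes the first ineffective as a restriction for members of that group.

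**The case against.** The mismatch can be called editorial. Three places are permissive, 9.4.1 gives the Sponsor the choice expressly and accepts the power consequence, and the decision rules can be read as fixing only the size of any increase. The low cost in overall power supports this. But 9.4.1 presents those rules as the possible outcomes of the interim, and none of them has conditional power in the zone with N unchanged. The texts still need to be reconciled.

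On access, the objection is that the point argues from silence. There are real safeguards: an independent statistician, the confidentiality sentence, randomization pre-programmed in the EDC system (Section 5.7), and image review of closure by an evaluator (Sections 3, 5.8 and 5.10). Sections 5.15.5 and 13.1 state an intent to discontinue only for valid scientific or administrative reasons, and the interim has no futility stop. Section 9.6 refers to a formal statistical analysis plan, which might define the group. All this tempers the risk. However, the confidentiality sentence limits spread beyond the group without restricting what its members do, and the text supplied contains no definition.

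A reader might infer that the Sponsor's option inflates type I error or leaves the trial underpowered. The calculations do not support either. A reader might also infer that sites receive interim results, or that the group's members do run the trial. No section says so; the plan only fails to exclude the latter.

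**Conclusion.** The point holds in two parts. First, the rule that fixes N in the promising zone is contradictory in both arms and unsettled before the unblinded effect is seen. Second, unblinded results go to a Sponsor group that the supplied text neither defines nor separates from trial conduct.

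The second part carries the weight. Its harm is a risk of operational bias and lost credibility, and its size cannot be derived from the documents. The first part moves the chance of success by about 11 to 12 points when the interim falls in the zone, but overall power by less than 2 points with all patients counted (up to 2.6 points with 20% loss). Overall power remains above 0.80 at the design rates. These figures assume the design rates, equal interim groups and the caps read as arm totals. The change should be made before the interim; it is not a failure of power or of error control.

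**What to change.** In Sections 9.4.1 and 9.4.2:

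- **Results.** State that interim results, Z and conditional power stay with the independent statistician until database lock, and that the Sponsor receives only the revised enrolment target. The target may go to the staff who put it into effect at sites, since Section 3 ties per-site maxima to it (27 to 41 DFU, 15 to 22 VLU). Note in the plan that the target allows an approximate inference about the effect.
- **Exceptions.** If any Sponsor person must see results, name that person by role and exclude the role from site management, monitoring, data review and completion of the analysis plan. Finalise the analysis plan, including the imputation variables left open in Section 9.6, before the interim.
- **One rule.** Align Sections 1, 3, 9.4.1 and 9.4.2 on either a binding increase, or a non-binding one with criteria fixed before the interim that do not depend on interim results.

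**Cost.** Wording, and loss of the Sponsor's sight of interim results. Only under a binding rule does the Sponsor also commit to more patients: on average about 46 (DFU) or 27 (VLU) when the interim falls in the zone, within the existing caps.

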9.4.2 VLU Arm

The interim analysis for the VLU arm will be performed independently of the interim analysis for the DFU arm, but it will be very similar in nature.

In the VLU arm, the analysis will be conducted when ~50% of the mITT population (30 patients) have been enrolled and completed the primary endpoint evaluation. The methods will be the same as described above. M` will not exceed 90 patients for the VLU arm.

The following decision rules outline the possible outcomes of the interim analysis:

1. If the test for CPni < 0.43 or ≥ 0.8 , then there is no increase in the sample size and the trial will be completed on a minimum of 60 enrolled patients, as scheduled.
2. If the test for conditional power is $0.43 \leq \text{CPni} < 0.8$, then the sample size will be increased by just the right amount such that CPni is increased to 0.8, under a cap of 90 patients. The range $0.43 \leq \text{CPni} < 0.8$ is called the promising zone for non-inferiority. Specifically, if CPni is in its promising zone, this decision rule increases the sample size by the smallest of 90 patients or the number needed to boost CPni to 0.8.

CP=Conditional Power
Probability of success (statistical significance) at the end of the trial given current data trend

9.5 Statistical Analysis

Data collected in this study will be reported using summary tables and patient data listings. Continuous variables will be summarized using descriptive statistics (number of patients, mean, standard deviation [SD], median, minimum, and maximum). Categorical variables will be summarized using frequencies and percentages of patients in each category. All results will be presented by treatment group and study arm in appropriate patient populations. SAS software version 9.4 or higher will be used for the statistical analysis.

9.5.1 Demographic and Baseline Characteristics

Patient demographics for all analysis populations will be summarized in a table. Gender, ethnicity, and race will be summarized with frequency and percent. Age, height, weight, and BMI will be summarized with N, mean, standard deviation, median and minimum and maximum.

9.5.2 Medical History

Patient medical history, including tobacco use, comorbidities, diabetes history, and wound history (where applicable) for all analysis populations will be summarized in a table. Categorical variables will be summarized with frequency and percent. Continuous variables will be summarized with N, mean, standard deviation, median and minimum and maximum.

9.5.3 Procedural Information

Descriptive statistics will be used to summarize the initial wound assessment by treatment group and procedural information.

9.5.4 Primary Endpoints

For the purpose of the primary endpoint analysis, the largest study wound will be analyzed.

9.5.4.1 DFU Arm

100% re-epithelialization will be assessed every week (except during virtual visits) for 12 weeks for DFU patients or until 100% re-epithelialization, whichever occurs first. Persistence of wound closure will be verified via confirmatory visit within 2 weeks after complete closure has been first determined.

For the primary endpoint of 100% re-epithelialization at week 12 a two-stage analysis will test first if the rate of 100% re-epithelialization is non-inferior between groups using a Farrington & Manning test. Noninferiority for synthetic hybrid-scale fiber matrix will be demonstrated if the lower bound of the 90% CI of the difference in proportions lies above the non-inferiority margin of -10%.

If non-inferiority is shown, superiority of synthetic hybrid-scale fiber matrix over Standard of Care will be tested using a chi-square test.

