5.7 Randomization

The randomization process will be pre-programmed into the electronic data capture (EDC system) prior to enrollment of the first study patient.

Once the patient meets all enrollment criteria and has completed the 2-week run-in period, the patient will be randomized. Patients with a DFU(s) will be randomized to receive either synthetic hybrid-scale fiber matrix (treatment group) or SOC (control group). Patients with a VLU(s) will be randomized to receive either synthetic hybrid-scale fiber matrix (treatment group) or living cellular skin substitute (control group).

Randomization will be stratified by wound size:

- DFUs will fall into two groups ($>1.0 \text{ cm}^2$ and $< 12.5 \text{ cm}^2$) and ($\geq 12.5 \text{ cm}^2$ and $< 25 \text{ cm}^2$). Patients within each group will be randomized in a 1:1 ratio to receive either synthetic hybrid-scale fiber matrix or SOC.
- VLUs will fall into two groups: ($>1.0 \text{ cm}^2$ and $< 25 \text{ cm}^2$) and ($\geq 25 \text{ cm}^2$ and $< 50 \text{ cm}^2$). Patients within each group will be randomized in a 1:1 ratio to receive either synthetic hybrid-scale fiber matrix or living cellular skin substitute.

Once the patient is ready to be randomized, the randomization form will be completed by study personnel in the electronic data capture (EDC) system. The randomization assignment will be obtained from the EDC system prior to the initial application of the study product. If a patient has more than one wound that meets all enrollment criteria, then all wounds will be randomized to the same study product. The largest wound that meets enrollment criteria will determine the size stratification for the patient.

Any patients that exit the study before randomization are considered screen failures. A study exit CRF shall be completed if the patient is not eligible for randomization.

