9.5.4.2 VLU Arm

100% re-epithelialization will be assessed every week (except during virtual visits) for 16 weeks for VLU patients or until 100% re-epithelialization, whichever occurs first. Persistence of wound closure will be verified via confirmatory visit within 2 weeks after complete closure has been first determined.

For the primary endpoint of 100% re-epithelialization at week 16 a Farrington & Manning test will be used. Noninferiority for synthetic hybrid-scale fiber matrix will be demonstrated if the lower bound of the 90% CI of the difference in proportions lies above the non-inferiority margin of -10%.

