9.6 Strategies to Address Missing Data

Patients who are missing complete wound closure will be considered as “missing data patients”. Missing complete wound closure status will be imputed using a logistic regression multiple imputation approach for dichotomous outcome data. In this approach, missing healing status will be imputed from logistic regression models with independent variables of age, gender, and other variables to be specified in the formal statistical analysis plan. This will be performed 50 times in each arm in order to generate 50 “complete” datasets. For the DFU arm, the one-sided Farrington & Manning test for assessing treatment difference will be carried out on each of the 50 complete datasets, with the results being combined across the 50 complete datasets using standard multiple imputation theory to obtain one overall p-value comparing the two treatments on the primary endpoint after accounting for missing data. Similarly for the VLU arm, the one sided Fisher’s Exact test for assessing treatment difference will be carried out on each of the 50 complete datasets, with the results being combined across the 50 complete datasets using standard multiple imputation theory to obtain one overall p-value comparing the two treatments on the primary endpoint after accounting for missing data.

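### Randomization is stratified by wound size but the confirmatory tests ignore the strata: a low-priority, inexpensive improvement, not an error

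*Combined protocol and SAP*

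**What the plan says.** Section 5.7 states: "Randomization will be stratified by wound size". DFU patients are split at 12.5 cm² and VLU patients at 25 cm², with 1:1 allocation inside each stratum. For patients with several wounds, "The largest wound that meets enrollment criteria will determine the size stratification for the patient". Section 9.5.4 adds: "For the purpose of the primary endpoint analysis, the largest study wound will be analyzed". Every analysed patient therefore already has a defined baseline stratum.

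The tests are named without strata:
- DFU non-inferiority (9.5.4.1): the plan will "test first if the rate of 100% re-epithelialization is non-inferior between groups using a Farrington & Manning test", judged by the lower bound of a 90% CI against -10%.
- DFU superiority (9.5.4.1): "superiority of synthetic hybrid-scale fiber matrix over Standard of Care will be tested using a chi-square test".
- VLU non-inferiority (9.5.4.2): "For the primary endpoint of 100% re-epithelialization at week 16 a Farrington & Manning test will be used".
- Imputed data (9.6): for DFU, "the one-sided Farrington & Manning test for assessing treatment difference will be carried out on each of the 50 complete datasets". For VLU a one-sided Fisher's exact test is named, also without strata.

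Section 9.5 says: "All results will be presented by treatment group and study arm in appropriate patient populations". No analysis in 9.5 or 9.6 is said to use the stratification factor. The hypotheses (9.1.1.1, 9.1.1.2), sample sizes (9.3) and interim statistic (9.4.1, also used in 9.4.2) rest on the same unstratified Farrington-Manning test.

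**The concern.** Stratified randomization removes chance imbalance in wound size between the groups. A crude test still counts the variation between strata as noise. If wound size is prognostic, the standard error is then too large for the design, the test runs below its nominal 5%, and some of the power that the stratification makes available is lost. Both comparisons are small and planned at 80% power, so a few points could matter.

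There is also a question of consistency. If a stratified analysis is run only after the data are seen, and the crude and stratified results fall on opposite sides of -10%, nothing in the plan says which one counts.

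**Working it through.** **1. The plan's sample sizes.** Inputs from 9.3.1 and 9.3.2: closure 75% vs 60% (DFU) and 75% vs 50% (VLU), margin 10 points, one-sided alpha 0.05, power 0.80, 20% loss to follow-up. The Farrington-Manning size per group is

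n = [(1.645·√V0 + 0.842·√V1) / (p1 − p2 + 0.10)]²,

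where V1 = p1(1−p1) + p2(1−p2), and V0 is the same sum at the rates restricted to a difference of −0.10.

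- DFU: restricted rates 0.6156 and 0.7156, V0 = 0.4402, V1 = 0.1875 + 0.2400 = 0.4275. n = [(1.0913 + 0.5505)/0.25]² = 43.1, so 44 per group. 88/0.8 = 110. Power at 44 is 0.807 (exact binomial 0.817).
- VLU: restricted rates 0.5663 and 0.6663, V0 = 0.4679, V1 = 0.1875 + 0.2500 = 0.4375. n = [(1.1253 + 0.5569)/0.35]² = 23.1, so 24 per group. 48/0.8 = 60. Power at 24 is 0.814 (exact 0.807).

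Both stated figures reproduce. The exact type I error of the crude test, with no size effect, is 4.6% (DFU) and 4.5% (VLU).

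**2. Mechanism.** Let q be the share of patients in the large-wound stratum and g the closure gap between strata. Assume the same g in both groups. The within-stratum variance is V1 − 2q(1−q)g². Take q = 0.30 as an assumption.

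- g = 0.20: 2 × 0.3 × 0.7 × 0.04 = 0.0168. Variance ratio for DFU: 0.4107/0.4275 = 0.96. VLU: 0.4207/0.4375 = 0.96.
- g = 0.40: 2 × 0.3 × 0.7 × 0.16 = 0.0672. DFU: 0.3603/0.4275 = 0.84. VLU: 0.3703/0.4375 = 0.85.

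**3. Simulation.** There were 400,000 trials per scenario. It used the plan's closure rates, q from 20 to 50%, random stratum sizes and allocation balanced within strata. The stratified statistic is the Mantel-Haenszel risk difference with a score variance including N/(N−1). It reverts to the crude test if either group has fewer than 5 patients in a stratum. The table gives the change in non-inferiority power, stratified minus crude, in points.

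| Assumed gap | DFU, 44 per group | VLU, 24 per group |
|---|---|---|
| 0 | −0.6 to −0.5 | −0.2 to −0.1 |
| 10 | −0.4 to −0.3 | +0.1 to +0.2 |
| 20 | +0.1 to +0.5 | +0.6 to +1.4 |
| 30 | +0.8 to +1.4 | +1.2 to +2.9 |
| 40 | +1.9 to +2.9 | +2.1 to +4.7 |

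Example with q = 30% and a 20-point gap. DFU: power 0.8217 crude and 0.8247 stratified, type I error 4.30% and 4.74%. VLU: power 0.8111 and 0.8224, type I error 4.22% and 4.73%. The break-even gap is about 14 to 19 points for DFU and about 5 points for VLU.

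At 55 and 30 per group (all enrolled patients analysed, imputation variance ignored), crude power is already 0.88 to 0.91. The gains there are +0.2 to +0.3 (DFU) and +0.4 to +0.8 (VLU) at a 20-point gap, and +1.5 to +2.1 and +1.9 to +3.0 at 40 points.

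**4. DFU superiority.** The plan gives no sidedness, so two-sided 0.05 is assumed. Chi-square power at 44 per group is 0.32 to 0.34. A Cochran-Mantel-Haenszel test changes it by −1.1 to −1.0 points with no gap, 0.0 to +0.4 at 20 points and +3.4 to +6.2 at 40 points.

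**5. Type I error.** With balanced allocation the crude test runs at 3.2 to 5.0% and the stratified test at 4.1 to 5.2%. With unblocked allocation the ranges are 4.9 to 5.2% and 4.95 to 5.35%. A stratified version without the N/(N−1) factor and without the sparse-stratum rule reached about 6.0% in the worst VLU scenario (50-point gap, 20% large).

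**6. Interim.** The adaptive design was simulated with the plan's conditional-power and re-estimation formulas, the cap read as 83 (DFU) or 45 (VLU) per group, and balanced allocation. A crude interim followed by a stratified final test had type I error of 4.65 to 4.98% (DFU) and 4.31 to 4.87% (VLU). Stratifying the interim as well changed power by at most 0.2 points.

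**The case against.** The case for leaving the plan alone is strong. The crude test is valid and delivers its stated power, and the plan uses one Farrington-Manning statistic for hypotheses, sizing, interim and final test. The documents give no stratum shares, closure rates by size or block size, so no benefit can be demonstrated. At a 20-point gap the DFU gain is at most half a point, and below the break-even gap stratifying costs power. With exactly balanced strata the Mantel-Haenszel difference equals the crude difference, so the gain comes from bringing a conservative test closer to 5%, not from a better estimate. For VLU at 24 per group, the minimum-of-5 rule would revert to the crude test in about 50% of analyses if 20% of wounds are large, and in 98% if 10% are.

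All of this stands, and it sets the weight of the point. It does not remove the mismatch or the value of settling the choice in advance.

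A reader might infer that ignoring the strata inflates the false-positive rate or leaves the trial underpowered. Sections 9.3.1 and 9.3.2 reproduce, and the crude type I error stays near or below 5%, so neither follows. A reader might also count wound size as missing from the imputation model. Section 9.6 defers further variables to a formal SAP, so it may still be included there.

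**Conclusion.** The point holds as a low-priority improvement in efficiency and consistency, not as an error. If wound size clearly predicts closure and allocation is balanced, the crude test is conservative: about 3.2 to 3.8% type I error at an assumed 40-point gap, with about 2 to 5 points of power lost at 44 and 24 per group. At 20 points the loss is about 0 to 1.5 points. With no gap the crude test is better by up to about 0.6 points, or about 1 point for DFU superiority.

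These figures assume the plan's closure rates, the same size gap in both groups, and 20 to 50% of patients in the large stratum. If only 10% are, the change is between −0.2 and +0.5 points (DFU) and 0.0 and +0.2 points (VLU) at every gap from 0 to 40.

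The difference between Fisher's exact test in 9.6 and Farrington-Manning in 9.5.4.2 for VLU is a separate matter and is not part of this conclusion.

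**What to change.** - In 9.5.4.1 and 9.5.4.2, base the final non-inferiority test and its 90% CI on the wound-size-stratified Mantel-Haenszel risk difference, with a stratified score variance that includes the N/(N−1) factor. Change 9.1.1.1 and 9.1.1.2 to match, since both name the plain Farrington-Manning test.
- Use a Cochran-Mantel-Haenszel test for DFU superiority.
- In 9.6, apply the same stratified statistic to each imputed dataset, and list the wound-size stratum among the imputation variables.
- Before the interim, pre-specify a sparse-stratum rule, for example reverting to the crude test if either group has fewer than 5 patients in a stratum.
- Keep the crude test as a sensitivity analysis.
- The sample sizes in 9.3 and the interim statistic in 9.4 may stay crude, provided the plan says so.

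The cost is wording and some SAS code, with no new data. The plan should state the downsides: a small power loss if size is weakly prognostic (up to about 0.6 points with balanced allocation; 0.7 for DFU or 0.9 for VLU if unblocked), type I error up to about 5.2% balanced or 5.35% unblocked, and frequent reversion to the crude test in VLU if few wounds are large.

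If the sponsor prefers to keep the crude tests as primary, a stated reason and a pre-specified stratified sensitivity analysis would also settle the inconsistency.
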